Principal Investigator: [name].

Protocol 12-DA-N474: Identifying neurological mechanisms that underlie acute nicotine withdrawal and drive early relapse in smokers.

Approval Date: March 2, 2022

NCT 01511614

Date: March 2, 2022

Principal Investigator: [name].

Protocol Title: Identifying neurobiological mechanisms that underlie acute nicotine withdrawal and drive early relapse in smokers.

Abbreviated Title: Neurobiology of nicotine withdrawal

Protocol Number: 12-DA-N474

Date of This Submission/Version: March 2, 2022

Principal Investigator:

T Time par in vesti	B			
Name, Degree	Branch/Institute	Bldg/Rm	Phone/Fax	Email
[name]	NIDA/IRP//NRB	BRC/07A709 [name]	P: [contact] F: [contact]	[contact]

Total requested accrual:

Total Enrollees: 577 Completers: 500

Main Study:

120 Treatment-seeking smokers (enrollees), 85 Completers

42 non-treatment seeking smokers (enrollees), 35 completers.

Motivational Interviewing Arm:

300 people interested in quitting smoking, but not yet ready to set a quit date.

Transcranial Direct Current Stimulation (tDCS) arm:

60 non-treatment seeking smokers (enrollees), 35 completers

55 nonsmokers (enrollees), 45 completers. Up to the first 25 of these enrollees will complete the tDCS without MRI (Behavioral Pilot)

Project Uses Ionizing Radiation:	¥ No	☐ Yes
IND/IDE	₩ No	□Yes
Durable Power of Attorney	₩ No	☐ Yes
Multi-institutional Project	₩ No	☐ Yes
NIDA is the coordinating site		
Data and Safety Monitoring Board	¥ No	□ Yes

Date: March 2, 2022

Principal Investigator: [name].

Technology Transfer Agreement ☐ No ☐ Yes MTA with LSU for plasma	samples. Expires Γ	December 12, 2022.	
Samples are being stored samples acquired for measurement assays have been obtained.		Yes (temporarily, page 1.25) ACTH will be destroyed once	L
Flesch-Kincaid reading level of con- (exclude boilerplate in assessing rea			

Medical Coverage Level:

Level 5 - The MAI (or designated clinician) is available by beeper or phone.

**

- **Level 1** The MAI administers all drugs and remains physically present in the experimental room during all or part of study session as determined by the Clinical Director.
- **Level 2** The MAI must be physically present in the experimental room during all or part of study session as determined by the Clinical Director.
- Level 3 The MAI must be present within the study building.
- Level 4 The MAI must be on the study campus.
- Level 5 The MAI is available by beeper or phone.

Principal Investigator: [name].

Précis:

Objective

The primary objective of the current protocol is to gain a greater understanding of the neurobiological mechanisms underlying acute nicotine withdrawal and contributing to the maintenance of, or return to smoking behavior among nicotine-dependent individuals, in the service of developing future smoking cessation treatments. The Nicotine Withdrawal Syndrome is a major cause of failed quit attempts in smokers, and targeting this time period for intervention may help improve smoking cessation outcomes.

Study Population

We will recruit treatment seeking and non-treatment seeking smokers, as well as matched non-smoker control participants.

Design

There are 3 arms included in this protocol, each of which aims to understand the neurobiology of the Nicotine Withdrawal Syndrome during the initial quit period, with the broader goal of increasing quit success rate in the future.

Main Study: To understand (1) the acute neurobiological effects of nicotine withdrawal on treatment-seeking and non-treatment seeking smokers, (2) the long term neurobiological outcomes of varenicline treatment and smoking cessation counseling at 1, 6, and 12 months. We will recruit 85 treatment seeking and 35 non-treatment seeking smokers for a within (nicotine deprivation), between (treatment-seeking status) subjects randomized, double blind, placebo controlled study.

Motivational Interviewing Arm: (1) To increase motivation and preparation for smoking cessation treatment among individuals who express an interest in quitting smoking but are not currently ready to enter treatment, in the service of increasing quit success rate and (2) to understand the neurobiological basis of motivation to quit smoking, and the interaction between motivation to quit and mechanisms that underlie acute nicotine withdrawal. We will recruit 300 current smokers interested in quitting smoking, but not yet ready to set a quit date.

Transcranial Direct Current Stimulation (tDCS) Arm: To understand the acute effect of tDCS on 3 large-scale brain networks dysregulated in nicotine addiction and withdrawal, the Default Mode Network, the Executive Control Network, and the Salience Network. We will enroll 60 non-treatment seeking smokers, with the expectation of 35 completers; and enroll 55 non-smoking controls, with the expectation of 45 completers, for a double blind, sham controlled, randomized crossover study. Smokers will be studied in nicotine abstinence and nicotine sated conditions, as in the Main Study design.

Principal Investigator: [name].

Outcome measures

Primary outcome measures:

- 1) Change in BOLD signal and FC related to task parameters, between drug (or tDCS) condition.
- 2) Behavioral performance on each of the tasks assessing inhibitory control processes, reward responsiveness, amygdala, striatal, BNST reactivity, impulsive decision making, cue reactivity and working memory (e.g., reaction time, error rate, hit rate, reward bias).
- 3) Self-reported craving, withdrawal symptoms and mood/affect
- 4) Smoking abstinence as determined by self-reported tobacco use, urine cotinine, and breath CO.

Secondary outcome measures:

- 1) MRS for glutamate concentration.
- 2) Plasma ACTH and cortisol.
- 3) Resting state CBF from ASL.
- 4) ERP and EEG measures.
- 5) Ratings and scores on self-report characterization measures.
- 6) Structural MRI and DTI data.
- 7) Resting state FC at 1, 6 and 12 months post-treatment.

Table of Contents

Objec	ctive	4
Outco	ome measures	5
List of Abl	breviations	10
1. Introduc	ction/Scientific Rationale	11
1.1.	Anhedonia during acute nicotine withdrawal: neurobiological mechanisms	12
1.2.	Stress reactivity and negative affect during acute nicotine withdrawal:	
neurobiologic	cal mechanisms	13
1.3.	The Brain's Default Mode Network: Does it play a role in acute nicotine	
withdrawal?	14	
1.4.	Inhibitory control and impulsive decision making during acute nicotine	
1	potential neurobiological mechanisms	15
1.5.		
1.6.	Transcranial Direct Current Stimulation	
1.7.	Considerations when conducting nicotine-withdrawal research	
	bjectives or hypotheses	
	view	
	y population	
	gn	
•	Primary goals	
2.1. 2.2.	• •	
	, ,	
2.3.	Aims and hypotheses	
•	S	
3.1.	Study population	
3.2.	Inclusion criteria	
3.3.	Exclusion criteria	
•	esign and Methods:	
4.1.	Study overview	
4.2.	Recruitment	
4.3.	Screening methods	
4.4.	Study procedures	
4.5.	End of participation	

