3) Other issues or concerns expressed by participants regarding the treatment schedule. If any participant expresses concerns or experiences issues regarding attendance at counseling sessions or varenicline administration (e.g., no longer wishes to receive varenicline treatment) we will work with the individual participant to derive a treatment plan that is suitable for them. This will help participants remain in treatment for the full 12-weeks. For example, if any participant wishes to discontinue varenicline treatment but still wishes to attend the counseling sessions, they will be offered NRT as an alternative treatment, but may still continue the counseling sessions in the event that they refuse NRT. Alternatively, if a participant wishes to continue varenicline treatment but has issues/concerns with attendance at counseling sessions, they can continue to receive varenicline treatment without counseling. However, we will require that at a minimum they attend NIDA-IRP at least biweekly to pick up their weeks supply of varenicline, complete a nurse assessment, complete their questionnaires

Principal Investigator: [name].

and receive a brief medical monitoring and abstinence assessment from a study therapist. During the weeks that participants do not come in, study therapists will call participants to conduct telephone assessments to monitor for changes in physical and psychiatric symptoms (administering the varenicline toleration assessment) and assess smoking status.

Date: March 2, 2022

Participants do not wish to attend follow-up visits. If a participant is contacted at the 1, 6 or 12 month follow-up time point and at this point states they do not wish to attend a follow-up visit, they will be asked to complete a part of their follow-up assessment over the phone. The assessment will be conducted by one of the study therapists who will assess the participants quit status and smoking history since their last contact with the study team.

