10.1. Primary outcomes measures

1) Change in BOLD signal and FC related to task parameters, between drug conditions: will provide important insight into the neurobiological mechanisms underlying acute nicotine withdrawal, in particular those related to anhedonia, negative affect, inhibitory control and impulsive decision making.

Date: March 2, 2022

- 2) Behavioral performance on each of the tasks assessing inhibitory control processes, reward responsiveness, amygdala, striatal, BNST reactivity and impulsive decision making (e.g., reaction time, error rate, hit rate, reward bias): will provide task-related parameters necessary for analysis of BOLD data. Performance data will function as a secondary outcome by providing behavioral validation of acute nicotine withdrawal effects.
- 3) Self-reported craving, withdrawal symptoms and mood/affect: will be employed as regressors in the analysis of task and resting BOLD data. They will also provide the primary means of validating the acute nicotine withdrawal manipulation.
- 4) Smoking status at 1, 6 and 12 months: Smoking status (relapse vs abstinent) at each of the follow-up time points will be based on 7-day point prevalence defined as no smoking (not even a puff) or use of any tobacco products for the past 7 days. This is a standard method of assessing abstinence and dichotomizing relapse status at follow-up (Keating & Siddiqui, 2006; Leventhal et al., 2008; Swan et al., 2010b). Whenever abstinence at follow-up is assessed in-person, self-reported abstinence will be corroborated with breath CO and urine cotinine levels.

10.2. Secondary outcome measures include:

- 4) MRS for glutamate concentration: Glutamate concentration at the PFC and hippocampus is expected to change as a function of acute nicotine withdrawal and may also play a role in the expected reduction in VS reactivity and anhedonia.
- 5) Plasma ACTH and cortisol: are expected to increase as a function of acute nicotine withdrawal and is expected to play role in both anhedonia and negative affective symptoms, potentially by acting at the amygdala, BNST and VS.
- 6) Resting state CBF from ASL: To test for changes in neural activity (i.e., not connectivity) at rest it is necessary to employ a measure which does not require a baseline. CBF provides such a measure as changes in blood flow are referenced to a common arterial location outside of the brain.

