RSN dynamics under acute nicotine withdrawal. The presence of three independent RSNs resembling the ECN, DMN and SN will be confirmed by applying an Independent Component Analysis (ICA) to the band pass filtered (0.01 to 0.08 Hz) resting BOLD time-series. ICA analysis will be conducted using the FSL Melodic ICA software (http://www.fmrib.ox.ac.uk/analysis/research/melodic/). The time-series of six seed regions reflecting core-nodes within each of these networks (ECN: dlPFC, PPC; DMN: vmPFC, PCC; SN: dACC, anterior insula) will then be regressed against each other to assess within and between network rsFC. Fisher r to z transformations will be applied to assess changes in rsFC between nicotine-deprived and non-deprived conditions. Bivariate partial correlations (controlling for nicotine dose) will also be conducted between the degree of change in rsFC within/between the three networks and changes in self-reported affective/cognitive withdrawal symptoms/urge to smoke as well as changes in working memory and attention indices. Treatment seeking status (Treatment seeking vs non-treatment seeking) will be included as a between-subjects factor in these models to assess the main effects and of motivation to quit as well as any interaction between motivation to quit and acute nicotine withdrawal. Correlations will be conducted separately for non-treatment and treatment seeking groups.

Principal Investigator: [name].

Relapse vs non-relapse group comparisons. Neurobiological processes underlying acute nicotine withdrawal will be assessed as a function of relapse status at each of the follow-up time-points by conducting between group comparisons.

Date: March 2, 2022

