Relapse vs non-relapse group comparisons. Based on previous studies comparing individuals who relapse following smoking cessation treatment to those who remain abstinent (Janes et al., 2010; Versace et al., 2011), we anticipate a medium-large effect size (Cohen's d = 0.65) when comparing relapsers vs non-relapsers across each of our neurobiological outcome measures. As we have proposed clear directional hypotheses regarding the relationship between treatment outcomes and neurobiological changes resulting from acute nicotine withdrawal, a one-tailed *t*-test model was used to calculate power. A power level $(1-\beta)$ of 0.8 was selected to achieve an appropriate balance between the ability to detect significant differences and the number of participants needed. Approximately 30 participants per group will be required to detect significant differences between these two independent groups at a nominal α level of 0.05 in a one-tailed test assuming a medium-large effect size (calculated by G*Power, http://www.psycho.uni-duesseldorf.de/abteilungen/aap/gpower3/).

Nicotine-deprived vs non-deprived condition comparisons. Estimating a dose-matched nicotine vs placebo effect size in 36 hr deprived smokers is complicated by several factors. Firstly, previous within-subject nicotine vs placebo studies have employed significantly shorter abstinence periods (e.g., 3 - 4 Hahn, Hong, Cole, or 8 hrs, Cole and Beaver). Secondly, studies addressing acute nicotine withdrawal effects using longer abstinence periods (e.g., 24 hrs) typically compare smoking deprivation to a smoke adlib condition (Azizian et al., 2010b; Field, Santarcangelo, Sumnall, Goudie, & Cole, 2006b; Kozink, Kollins, & McClernon, 2010b; McClernon et al., 2008b; McClernon, Kozink, Lutz, & Rose, 2009a; Mitchell, 2004b). Following 8 hrs of smoking deprivation, nicotine (relative to placebo) produces small to medium effects on self-report withdrawal symptoms, mood and craving measures (Cohen's d = 0.15 to 0.52), medium effects on behavioral measures (d = 0.48 to 0.618) (Beaver et al., 2011; Cole et al., 2010). Effects of 12 to 24hrs of smoking deprivation (relative to adlib smoking) on self-reported craving and affect/mood vary from medium to large (d = 0.51 to 4.91). The same deprivation periods produce small to medium effect sizes (d = 0.23 to 1.435) for go-nogo, attention and delay discounting tasks with larger effects on RT and discounting rate and smaller effects on error rates.

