11.5. Accrual number request, taking into account screening/dropouts

Treatment-seeking smokers. In the current study, an individual will be considered a completer if they meet the following criteria: 1) have completed the two pre-treatment scan visits; 2) have set a quit date; 3) attempted to quit for at least 24 hours; 4) we have been able to establish their quit status (i.e., relapsed vs non-relapse) at 1, 6 and 12 months following their last treatment visit. Based on the power analyses above we anticipate that a minimum group size of 30 in each of our two relapse groups (relapse vs abstinent) at each follow-up time point (1, 6 and 12 months) would provide a reasonable level of statistical power allowing for the detection of effects of interest in the present study. Based clinical trials of varenicline with similar follow-up time points (Aubin et al., 2008; Keating & Siddiqui, 2006; Krebs & Sherman, 2012; Swan et al., 2010a; Tsai et al., 2007), we estimate that 35% of completers at 12 months will meet criteria for 7-day point prevalent abstinence. The 12 month follow-up is the point at which we would expect our abstinent group to be smallest. Achieving a minimum of 30 abstinent smokers at 12 months would require 85 completers (i.e., 35% abstinence rate). Based on an expected 30% attrition rate at 12 months (Keating & Siddiqui, 2006) a total of 120 treatment-seeking smokers (85 completers) is therefore requested.

Non-treatment seeking smokers. An individual will be considered a completer if they complete procedures outlined for Phase 1 of the protocol (see Section 4 Study Design and Methods). Based on power analyses described above and in Section 10.4 we anticipate that 35 non-treatment seeking smokers with complete

Principal Investigator: [name].

Date: March 2, 2022

and useable data would provide a reasonable level of statistical power allowing for the detection of effects of interest in the present study. However, since acute nicotine-withdrawal effects may increase head movement and given the potential for unforeseeable errors during data collection, an estimated 20% of the participants who complete all phases of the study will likely be removed from the final analyses. Thus, a total of 42 non-treatment seeking smokers is requested.

12. Human Subjects Protection

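### Abstinence reported only by phone is never biochemically checked, yet nothing keeps it out of the abstinent group in the relapse comparison that sizes the treatment-seeking cohort

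*Combined protocol and SAP*

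**What the plan says.** The précis, under primary outcome measures, gives item 4 as "Smoking abstinence as determined by self-reported tobacco use, urine cotinine, and breath CO", with no exception stated.

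Section 10.1 item 4 is the working definition. Smoking status at 1, 6 and 12 months is "based on 7-day point prevalence defined as no smoking (not even a puff) or use of any tobacco products for the past 7 days". It then adds: "Whenever abstinence at follow-up is assessed in-person, self-reported abstinence will be corroborated with breath CO and urine cotinine levels".

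Section 4.4, under potential problems and alternatives, covers participants who do not want to attend a follow-up visit: "they will be asked to complete a part of their follow-up assessment over the phone". The call is made by a study therapist "who will assess the participants quit status and smoking history since their last contact with the study team". No sample and no later check is described.

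Section 11.5 counts a treatment-seeking participant as a completer if, among other conditions, "we have been able to establish their quit status (i.e., relapsed vs non-relapse) at 1, 6 and 12 months". Section 9.3 has a similar condition. Neither asks for verification.

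Section 11.2 uses the classification directly: neurobiological measures "will be assessed as a function of relapse status at each of the follow-up time-points by conducting between group comparisons". Section 11.4 sizes that comparison: "we anticipate a medium-large effect size (Cohen's d = 0.65) when comparing relapsers vs non-relapsers".

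**The concern.** Biochemical checking is absent for exactly those people who chose not to come in, and that choice may well be related to smoking. Two people with the same smoking behaviour can end up in different groups because one attended and gave a sample while the other answered a phone call. A relapsed smoker who claims abstinence by phone joins the abstinent group and brings its mean closer to that of the relapsers.

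Hypotheses 1.1, 2.4, 4.1 and 4.2 (Section 2.3) all link withdrawal-related change to treatment success, so they depend on this grouping. The protocol does not rely on self-report alone elsewhere. Inclusion criterion 5 in Section 3.2 prefers cotinine to reported cigarette use as a measure of exposure, and Section 4.4 has participants film their CO readings to validate a 36-hour abstinence period.

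**Working it through.** **Inputs from the documents.** d = 0.65, alpha 0.05 one-tailed, power 0.80 and 30 per group (Section 11.4). A 35% abstinence rate, 85 completers, 30% attrition and 120 enrolled (Section 11.5).

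**Reproducing the plan's figures.**
- Power is taken from the noncentral t distribution with df = n1 + n2 − 2 and noncentrality d × √(n1·n2/(n1 + n2)). With 30 per group and d = 0.65, one-tailed power is 0.800, so the stated 30 reproduces.
- Completers: 30 / 0.35 = 85.7, and 85 × 0.35 = 29.75, or about 30 abstinent and 55 relapsed.
- Enrolment: 85 / 0.70 = 121.4, and 120 × 0.70 = 84. The stated 120 is within rounding.
- At the expected 30 versus 55 split, noncentrality is 0.65 × √(30 × 55 / 85) = 2.86 and one-tailed power is 0.884.

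**Effect of false abstainers.** Suppose k of the 30 recorded abstainers are smokers who respond like relapsers. The expected difference becomes 0.65 × (1 − k/30), with the within-group SD held at 1. The values of k are assumptions.

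| k of 30 | expected d | power, 30 vs 55, one-tailed | power, 30 vs 30, one-tailed | power, 30 vs 55, two-sided |
|---|---|---|---|---|
| 0 | 0.650 | 0.884 | 0.800 | 0.808 |
| 1 | 0.628 | 0.865 | 0.776 | 0.781 |
| 3 | 0.585 | 0.819 | 0.724 | 0.722 |
| 4 | 0.563 | 0.793 | 0.695 | 0.689 |
| 6 | 0.520 | 0.735 | 0.635 | 0.620 |

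At 30 versus 55, power stays above the planned 0.80 up to 3 false abstainers and falls below it at 4. At 30 per group there is no slack.

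**Cost of leaving phone-only claims out of the abstinent group** (d stays 0.65; 6 or 9 such claims assumed).
- 24 versus 55: 0.839 one-tailed, 0.747 two-sided.
- 21 versus 55: 0.807 one-tailed, 0.706 two-sided.
- If none of the claims is false, the one-tailed loss is 0.884 − 0.839 = 0.045 or 0.884 − 0.807 = 0.077. Two-sided it is 0.808 − 0.747 = 0.061 or 0.808 − 0.706 = 0.102.
- Break-even is near one third false. With 2 of 6 false, keeping the claims gives 0.843 one-tailed against 0.839 for leaving them out. With 3 of 9 it is 0.819 against 0.807. Above that share, leaving them out gains power; below it, the cost grows to the figures in the previous line.

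**Other ways of handling them** (one-tailed).
- Counting 6 or 9 true phone claims as relapsed gives 0.779 or 0.712.
- Restricting both groups to attenders, if the phone share is 20%, 30% or 40% in each, gives 0.813, 0.765 or 0.706.

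**The case against.** **The précis and Section 10.1 need not conflict.** A reader might infer that the two rules class the same phone claimant differently. The documents do not support that. The précis item is a one-line list of data sources; it does not say that all three are required, or what follows when an assay is missing. Section 10.1 limits corroboration to in-person assessment openly, and this fits Section 4.4. The objection stands: what is missing is a handling rule, and the précis wording needs aligning.

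**The effect may be small.** Nothing in the documents shows that phone follow-up is common or that claims are false. On the planned one-tailed test at the expected split, three false abstainers still leave power at 0.82. This also stands, and the figures above are scenarios only.

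**Excluding phone claims has its own bias.** If phone claims of abstinence are dropped while phone reports of smoking count as relapse, non-attenders can enter only the relapse group. Misclassification is then exchanged for selection that depends on the reported outcome. This stands too, so exclusion cannot be the only analysis.

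**Cotinine can mislead.** Section 4.4 offers patches and lozenges to those who stop varenicline. Someone still using them could test cotinine-positive while meeting the no-tobacco definition in Section 10.1. Section 4.4 gives a CO threshold (4 ppm or more is positive) for treatment visits, but no cotinine threshold for abstinence at follow-up. A simple all-three-sources rule would therefore misclass some participants.

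None of this supplies the missing rule. Following Sections 4.4, 10.1 and 11.5 as written still places an unverified phone claim in the abstinent group, with no sensitivity analysis.

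**Conclusion.** The concern holds in this form: unverified phone claims enter the abstinent group, and any that are false shrink the relapse versus non-relapse difference. With 3 to 6 false abstainers among 30, the expected d falls from 0.65 to between 0.585 and 0.52, and one-tailed power at 30 versus 55 falls from 0.88 to between 0.82 and 0.73. This rests on assumed counts, on false abstainers responding like relapsers, and on an unchanged within-group SD. The gap in the rule does not depend on those assumptions.

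Three wider readings are not supported. The comparison does not size the whole trial: it sets the 120 treatment-seeking smokers out of 577 enrollees, and the non-treatment-seeking and tDCS groups rest on other calculations. The stated 30 per group is not an arithmetic error. Nor is exclusion of phone claims a nearly free cure: it costs the most when the claims are true, and it introduces selection by attendance.

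This should be corrected before outcomes are examined, because a rule chosen later could move people between groups with results known.

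**What to change.** In Section 10.1 item 4 and Section 11.2:

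1. Record verification status (in person with assays, or phone only) for every participant at each follow-up.
2. Prespecify the relapse comparison with abstinence biochemically verified.
3. Alongside it, run the comparison with phone-only claims counted as abstinent, with them counted as relapsed, and restricted to in-person attenders in both groups.
4. Report the number of phone-only claims at 1, 6 and 12 months.
5. State the follow-up CO and cotinine thresholds and how disagreement with self-report is resolved. For anyone still using nicotine replacement, let CO plus self-report decide.
6. Align the précis wording with Section 10.1.

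No new visits or samples are needed, and phone follow-up stays. The work is one recorded field, a written classification rule and three extra runs. The statistical price is a smaller verified group: one-tailed power of 0.84 or 0.81 if 6 or 9 phone claims are left out. Selection by attendance remains possible; the parallel runs would show how far the conclusion depends on it.
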